	MDL Modello	Area: 01 Documento: MDL 01.01 Revisione: 0 Data di revisione: 18/04/2013 Pagina: 76 di 85
	Statistical Analysis Plan	
ANNEXIN 03		

Listing 16.2.8.2/1: Blood Chemistry

Subject ID	Visit	Have tests been done?	Sample collection date	Sample collection time	Parameter	Result	Unit	Abnormality
03-US-001	Screening	Yes	11/03/2011	10:52	ALT	U/L	XX	Abnormal Non-Clinical Relevant
					AST	U/L	XX	
					Etc...			
	Visit 3	Yes	09/04/2011	15:00				
03-US-002	Screening	Yes	10/07/2011	09:38				
03-US-003	Visit 3	No: XXXXX						

	MDL Modello	Area: 01 Documento: MDL 01.01 Revisione: 0 Data di revisione: 18/04/2013 Pagina: 77 di 85
	Statistical Analysis Plan	
ANNEXIN 03		

Listing 16.2.8.3/1: Urinalysis

Subject ID	Visit	Have tests been done?	Sample collection date	Sample collection time	Parameter	Result	Unit	Abnormality
03-US-001	Screening	Yes	11/03/2011	10:52	Appearance	XX	XX	Abnormal Non-Clinical Relevant
					pH	XX	XX	Abnormal Non-Clinical Relevant
					Etc...			
	Visit 3	Yes	09/04/2011	15:00				
03-US-002	Screening	Yes	10/07/2011	09:38				
03-US-003	Visit 3	No: XXXXX						

	MDL Modello	Area: 01 Documento: MDL 01.01 Revisione: 0 Data di revisione: 18/04/2013 Pagina: 78 di 85
	Statistical Analysis Plan	
ANNEXIN 03		

Listing 16.2.8.4: Immunogenicity

Subject ID	Visit	Has venous sample been done?	Reason for non performance	Sample collection date	Sample collection time	anti-rhAnnexin V-128	
						IgG	IgM
PAT_PATNUMBER	VISIT_NAME	IM_YN	IM_YN_SP	IM_DATE	IM_TIME		
03-US-001	Screening	Yes		11/03/2011	10:52	Negative	Negative
03-US-001	Visit 3	Yes		09/04/2011	15:00		
03-US-002	Screening	Yes		10/07/2011	09:38		
03-US-003	Visit 3	No	XXXXXXXXXX				

	MDL Modello	Area: 01 Documento: MDL 01.01 Revisione: 0 Data di revisione: 18/04/2013 Pagina: 79 di 85
	Statistical Analysis Plan	
ANNEXIN 03		

Listing 16.2.9.1: Pregnancy Test

Subject ID	Sex	Age	Visit	Has the pregnancy test been performed?	Reason for non performance	Specify reason	Pregnancy test date	Pregnancy test time	Pregnancy test result
PAT_PATNUMBER	PAT_GENDER	PAT_AGEYEAR	VISIT_NAME	PT_YN	PT_NOTDONE	PT_NOTDONE_SP	PT_DATE	PT_TIME	PT_RESULT
03-US-001	Male	54	Screening	Not applicable					
03-US-001	Male	54	Visit 1	Not applicable					
03-US-002	Female	38	Screening	Yes			09/04/2011	12:00	Negative
03-US-002	Female	38	Visit 1	Yes			12/04/2011	11:00	Negative
03-US-003	Female	59	Screening	No	Menopause				

	MDL Modello	Area: 01 Documento: MDL 01.01 Revisione: 0 Data di revisione: 18/04/2013 Pagina: 80 di 85
	Statistical Analysis Plan	
ANNEXIN 03		

Listing 16.2.9.2/1: Physical Examination

[figure not shown]
Subject ID	Visit	Has the physical examination been done?	Reason for non performance	Physical examination date	Physical examination time	Any clinically relevant finding?	Specify		
							First finding	Second finding	Third finding
PAT_PATNUM BER	VISIT_NAME	PE_YN	PE_YN_SP	PE_DATE	PE_TIME	PE_RELFIND_Y	PE_RELFIND 1	PE_RELFIND 2	PE_RELFIND 3
03-US-001	Screening	Yes		09/04/2011	12:00	No			
03-US-001	Visit 3	Yes		09/05/2011	10:00	No			
03-US-002	Screening	Yes		06/05/2013	9:45	Yes	XXXXXXX	XXXXXX	XXXXXX

	MDL Modello	Area: 01 Documento: MDL 01.01 Revisione: 0 Data di revisione: 18/04/2013 Pagina: 81 di 85
	Statistical Analysis Plan	
ANNEXIN 03		

[figure not shown]
Listing 16.2.9.3: Vital Signs

Subject ID	Visit	Time point	Have vital signs been evaluated?	Reason for non evaluation	Vital signs evaluation date	Vital signs evaluation time	Systolic BP (mmHg)	Diastolic BP (mmHg)	Pulse rate (beats/min)
PAT_PATNUMBER	VISIT_NAME		VS_POST_YN	VS_POST_YN_SP	VS_POST_DATE	VS_POST_TIME	VS_POST_SBP	VS_POST_DBP	VS_POST_HR
03-US-001	Visit 1	Before IP admin	Yes		09/04/2011	12:00	165	99	77
		After Last Imaging Procedure	Yes		09/04/2011	12:00	165	99	77
03-US-002	Visit 1		Yes		12/04/2011	10:00	129	93	60
03-US-003	Visit 1		Yes		06/05/2013	9:45	147	68	76

	MDL Modello	Area: 01 Documento: MDL 01.01 Revisione: 0 Data di revisione: 18/04/2013 Pagina: 82 di 85
	Statistical Analysis Plan	
ANNEXIN 03		

11.2 Standard Tables

	MDL Modello	Area: 01 Documento: MDL 01.01 Revisione: 0 Data di revisione: 18/04/2013 Pagina: 83 di 85
	Statistical Analysis Plan	
ANNEXIN 03		

11.3 Standard Figures

The different lines on the figures should look different (e.g. dotted lines) rather than using different colours so that the lines can be distinguished when using a non-colour printer.

	MDL Modello	Area: 01 Documento: MDL 01.01 Revisione: 0 Data di revisione: 18/04/2013 Pagina: 84 di 85
	Statistical Analysis Plan	
ANNEXIN 03		

APPENDICES TO THE SAP TEMPLATE

11.4 Derived Data

The following derived data will be calculated and included in the listings or in the tables:

(1) Age

Subject age (years) will be derived as $([\text{visit date}] - [\text{birth date}]) / 365.25$ and truncated to the largest integer that is less than or equal to the calculated result. If birth date is not a complete date then it will be approximated using "01" as value for the day and "01" as value for the month.

(2) BMI

BMI (kg/m^2) will be automatically derived as $[\text{WEIGHT}] (\text{kg}) / ([\text{HEIGHT}] (\text{cm}) / 100)^2$ and rounded to the nearest decimal.

(3) Time from injection

Time from injection (min) will be derived as the difference between each imaging assessment (i.e. whole body planar imaging, abdomen SPECT/CT, lumbosacral SPECT/CT, sacroiliac SPECT/CT and spot SPECT/CT) time and injection time $[\text{WBPI1_TIME} / \text{WBPI2_TIME} / \text{ABD1_TIME} / \text{ABD2_TIME} / \text{LUMB1_TIME} / \text{LUMB2_TIME} / \text{SACRO1_TIME} / \text{SACRO2_TIME} / \text{SPOT1_TIME} / \text{SPOT2_TIME} - \text{ANN_TIME}]$.

(4) Adverse event duration

If the start and end dates of the adverse event are identical then "<1" day will be presented with the duration in hh:mm recorded in the eCRF if it is available. If times are available, the duration will be calculated as (end date/time - start date/time) and presented in days hh:mm. If at least one time is missing and if the duration is greater than 24 hours then it will be calculated as (end date - start date)+1 and presented in days. If the recorded end date is CONT. (for continuing), the end date will be listed as "ongoing" and the duration will be approximated as $\geq(\text{last attended visit date} - \text{start date}) + 1$ day(s). If the start date or the end date are partial the duration will be presented as a superior inequality $\geq \text{xx}$ day(s) (i.e. ≥ 2 where start date = 31JAN2004 and end date = FEB2004 or start date = JAN2004 and end date = 01FEB2004).

	MDL Modello	Area: 01 Documento: MDL 01.01 Revisione: 0 Data di revisione: 18/04/2013 Pagina: 85 di 85
	Statistical Analysis Plan	
ANNEXIN 03		

(5) Delay of onset

Delay of onset will be reported as the difference in days from the day of Annexin injection. If the start date of the adverse event is identical to the date of injection, then "1" day will be presented with the time to onset in hh:mm recorded in the eCRF if it is available. If the time to onset is greater than 24 hours then it will be calculated as (start date - injection date) and presented in days. If the start date is partial, the time since injection will be presented as a superior inequality (i.e. for an AE started in FEB2004 after the injection performed on 31JAN2004, the delay of onset will be "≥2" days).

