6.1.5.2 Missing or incomplete dates

Incomplete dates due to missing day will be recorded as full dates replacing the missing day with the first day of month (01). Incomplete dates due to missing day and month will be recorded as full dates replacing the missing day and month with the first day of month and first month of the year (01/January). The trial database will record the information about incomplete dates due to missing day or due to missing day and month.

Only the incomplete dates related to date of birth, SpA diagnosis date, medical history (date of diagnosis and end date), concomitant medications (start and end date) and AEs (start and end date) will be replaced according to the above rule.

Calculation, sorting or assignation based on dates, in case of incomplete dates, will be performed using the related full dates defined by the above rule.

In all listings, missing and incomplete dates will be reported as full dates. In all listings will be also reported the information about incomplete dates according to the following coding: missing value = full date, Day = missing day, Day&Month = missing day and month.

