6.1.13 Derived data

The derived data are variables which are calculated from the raw data in the eCRF and could not be included in the database (e.g.: Age, BMI, days from ^{99m}Tc-rhAnnexin V-128 injection). The formula used for derived data and the strategy for missing data are provided in Section 11.4.

	MDL Modello	Area: 01 Documento: MDL 01.01 Revisione: 0 Data di revisione: 18/04/2013 Pagina: 36 di 85
	Statistical Analysis Plan	
ANNEXIN 03		

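### SAP 6.1.5.2 and 11.4(1) complete a birth date with only the day missing in different ways, so the derived age can differ by one year depending on which rule is programmed

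*SAP*

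**What the plan says.** SAP 6.1.5.2 separates two cases. For a missing day: "Incomplete dates due to missing day will be recorded as full dates replacing the missing day with the first day of month (01"), so a recorded month is kept. For a missing day and month, it completes the date by "replacing the missing day and month with the first day of month and first month of the year (01/January"). The scope is explicit: "Only the incomplete dates related to date of birth, SpA diagnosis date, medical history" and some further dates. The rule is not only for display, because calculations, sorting and assignments based on incomplete dates "will be performed using the related full dates defined by the above rule".

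SAP 11.4(1) defines age as visit date minus birth date, divided by 365.25, "truncated to the largest integer that is less than or equal to the calculated result". It then adds its own rule: "If birth date is not a complete date then it will be approximated using" 01 for the day and 01 for the month. It does not distinguish a missing day from a missing day and month.

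SAP 6.1.13 gives age as an example of derived data and points to the second rule: "The formula used for derived data and the strategy for missing data are provided in Section 11.4". Nothing says which section prevails.

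The shell of Listing 16.2.4.1 (Demographics) has a partial-date column for birth date with separate codes for a missing day and for a missing day and month, so the day-only case is foreseen.

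**The concern.** Both sections claim the same calculation. When day and month are both missing they give the same date, 1 January. When only the day is missing, 6.1.5.2 gives the first of the recorded month and 11.4(1), taken at its word, gives 1 January of that year. For a December birth in a common year that moves the birth date back by 334 days. Because age is truncated to whole years, a shift of that size can change the reported age.

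Two programmers could each follow the SAP and list different ages for the same patient. The listing prints birth date and age in one row, and 6.1.5.2 requires the completed date to be shown. If the age column were filled by 11.4(1), someone recomputing age from the printed birth date could get a different answer. Listings are the only planned output after early closure (SAP 8), so this output is still to be produced.

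**Working it through.** The documents state no error rate and no count of partial birth dates, so there is no figure of the plan's own to reproduce. The check compares the two rules with each other and with the age from the full birth date.

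**Inputs**
- Age formula (SAP 11.4(1)): floor((visit date − birth date) / 365.25).
- Rule of 6.1.5.2, day missing: 01 of the recorded month.
- Rule of 11.4(1), read literally: 1 January of the birth year.
- Assumption, not in the documents: birth and visit dates are independent and uniform over the calendar year.

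**One patient.** Born 20 September 1975, visit on 15 March 2016, day of birth not recorded.
- Full date: 14,787 days / 365.25 = 40.48, age 40.
- 6.1.5.2 (1 September 1975): 14,806 / 365.25 = 40.54, age 40.
- 11.4(1) (1 January 1975): 15,049 / 365.25 = 41.20, age 41.

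**Analytic shares, only the day missing**
- 11.4 above 6.1.5.2: the visit month falls before the birth month. Probability (1 − 1/12)/2 = 11/24 = 45.8%.
- 11.4 above true age: the visit falls before the birthday in the calendar year. Probability about 1/2.
- 6.1.5.2 above true age: the visit is in the birth month but before the birthday. Probability about (1/12)(1/2) = 1/24 = 4.2%.
- These agree: 11/24 + 1/24 = 1/2.

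**Enumeration** of every birth day with every visit day, for visit years 2015 and 2016 and birth years 1950, 1965, 1975, 1976, 1985 and 1990, using the SAP formula:
- 11.4 one year above 6.1.5.2: 45.7% to 46.0%.
- 11.4 one year above true age: 49.7% to 50.0%.
- 6.1.5.2 one year above true age: about 4.0%.
- 11.4 below 6.1.5.2: never.

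**Dependence on the visit month** (visit on the 15th, 2016; births uniform over 1975):

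| Visit month | 11.4 above 6.1.5.2 | 11.4 above true age |
|---|---|---|
| January | 91.5% | 96.2% |
| March | 75.3% | 79.7% |
| June | 50.4% | 54.5% |
| September | 25.2% | 29.3% |
| December | 0% | 4.4% |

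**Scale in this study.** Even if all five patients had only the day missing, the expected number whose age differs between the rules would be 5 × 11/24 = 2.3. The documents do not show that any of them did.

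**The case against.** The best defence is that 6.1.5.2 already settles the matter. It names date of birth, has the completed date recorded, and says calculations use it. On that view the birth date is complete by the time age is derived, and the last sentence of 11.4(1) never applies. That sentence can also be read as putting 01 only in whichever part is missing, which agrees with 6.1.5.2. It stands in an appendix headed as belonging to the SAP template, so it may be generic text, whereas 6.1.5.2 is specific to this study.

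This shows which rule was probably intended, but it does not remove the conflict. Section 6.1.13 sends the reader to 11.4 for exactly this question, 11.4(1) does not limit itself to the missing part, and no precedence is stated.

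Three stronger readings are tempting and are not supported:
- That 46% of such patients would be reported too old. The 46% is how often the two rules disagree. The share too old against true age is about 50% under 11.4 and about 4% under 6.1.5.2, so the better rule also errs upward, though seldom. All these shares rest on the uniform-date assumption.
- That the age criterion is at risk. Eligibility is checked at screening, source records must hold the date of birth, and the criterion has its own variable (IC_2) in Listing 16.2.1.3. Nothing ties it to the age derived under 11.4.
- That birth date and age will certainly disagree in the listing row. The shell maps Age to PAT_AGEYEAR and does not mark it as derived, as other shells do for derived columns, while 6.1.13 calls age derived. The source is therefore unclear. The partial-date flag would also warn the reader.

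**Conclusion.** The two sections conflict, on their plain wording, for a birth date with only the day missing. Under independent, uniform dates the literal 11.4 age is one year above the 6.1.5.2 age in about 46% of such cases, between about 92% and 0% depending on the visit month, and never below it. Measured against true age, 6.1.5.2 is clearly the better rule.

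The consequence is minor. A reader might infer that baseline results or conclusions are affected, but the documents do not support that: the study was closed after five patients, only listings will be produced, efficacy endpoints will not be addressed, and there is no covariate or subgroup analysis. What could be wrong is a listed, descriptive age, by one year, for a patient whose day of birth was not recorded.

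**What to change.** Replace the last sentence of SAP 11.4(1) with: 'Incomplete birth dates are completed as in 6.1.5.2: day missing = 01 of the recorded month; day and month missing = 01 January.'

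At the same time, confirm whether the Age column of Listing 16.2.4.1 is filled from PAT_AGEYEAR or from the 11.4(1) derivation and, if from PAT_AGEYEAR, that the variable follows the same rule.

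The cost is one sentence and one check. Programming work should be little or none, but this cannot be confirmed from the documents, because SAP 11.5 lists only procedure names and no age code.

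### SAP 11.4(5) mixes two day conventions for delay of onset, so an untimed same-day event and a next-day event can both be listed as 1, and the partial-date example does not follow from the formula

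*SAP*

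**What the plan says.** SAP 11.4(5) opens with a general definition: "Delay of onset will be reported as the difference in days from the day of Annexin injection". Three specific statements follow:

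- **Same date.** Onset on the day of injection gets a fixed value: "then '1' day will be presented with the time to onset in hh:mm recorded in the eCRF if it is available".
- **More than 24 h later.** "it will be calculated as (start date - injection date) and presented in days".
- **Partial start date.** A lower bound is shown. The worked example has an injection on 31JAN2004 and an onset in FEB2004, and prints ≥2 days.

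SAP 11.4(4) sets the duration rules:

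- For an event contained in one date, "If the start and end dates of the adverse event are identical then '<1' day will be presented".
- With both times recorded, "the duration will be calculated as (end date/time - start date/time) and presented in days hh:mm".
- Where either time is absent and the event runs past 24 h, "then it will be calculated as (end date - start date)+1 and presented in days".

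Other sections bear on this. SAP 6.1.14 labels the injection day Day 0. SAP 6.1.5.2 sets a missing day to the first of the month and uses the completed date in calculations. SAP 8 limits the output to subject data listings and a short close-out report. The shells for Listings 16.2.7.1 to 16.2.7.4 carry derived onset and duration columns but no adverse event start or end date. The onset column is headed *Day of onset* in 16.2.7.1 and *Delay of onset* in 16.2.7.2 to 16.2.7.4.

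**The concern.** The general definition and the formula for later events count the injection day as 0. The same-date value and the partial-date example count it as 1. A programmer who follows the text literally produces one column with two origins.

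This matters because the listings are the planned output and the shells do not show the raw event dates. A reader who sees a delay of 1 cannot work back to the start date, even though the injection date is in Listing 16.2.5.1. The plan itself treats the first day after a single injection as a distinct period: it schedules a 24-hour contact about reactions such as rash and edema. Whether an event began on the injection day or the next day is therefore something the listing should show. The two column labels add to the doubt, since a day number and a delay commonly differ by one.

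**Working it through.** **Inputs.** All rules and example dates come from SAP 11.4(4), 11.4(5) and 6.1.5.2. The March dates below are illustrative.

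**1. The plan's own examples.**
- Duration example, start 31JAN2004, end FEB2004, earliest end 01FEB2004: (01FEB − 31JAN) + 1 = 2. The printed ≥2 is reproduced.
- Onset example, injection 31JAN2004, onset FEB2004, completed to 01FEB2004: 01FEB − 31JAN = 1. The printed ≥2 is not reproduced. It appears only if a day is added: 1 + 1 = 2.
- Consequence: an event known to start on 01FEB2004 is listed as 1. The same event with its day missing is listed as ≥2, which excludes 1.

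**2. Onset values for an injection on 1 March at 10:00.**

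| Onset | Hours after injection | Rule that applies | Listed value | Injection day = 0 | Injection day = 1 |
|---|---|---|---|---|---|
| 1 March 11:00 | 1 | same date | 1 | 0 | 1 |
| 2 March 08:00 | 22 | general sentence only | 1 | 1 | 2 |
| 2 March 11:00 | 25 | formula beyond 24 h | 1 | 1 | 2 |
| 3 March 11:00 | 49 | formula beyond 24 h | 2 | 2 | 3 |

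The first and third rows collide under explicit rules. The second has no explicit formula and is 1 only through the opening sentence. Either consistent convention, in the last two columns, separates the dates.

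**3. Duration with and without times.**

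| Event | Timed (elapsed) | Untimed (inclusive days) | Excess in days |
|---|---|---|---|
| 1 March 10:00 to 2 March 11:00 | 1 day 01:00 | 2 | 0.958 |
| 1 March 10:00 to 3 March 10:00 | 2 days 00:00 | 3 | 1.0 |
| 1 March 23:00 to 3 March 01:00 | 1 day 02:00 | 3 | 1.917 |
| 1 March 01:00 to 3 March 23:00 | 2 days 22:00 | 3 | 0.083 |

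Let the end date be *n* days after the start date. The untimed value is *n* + 1. To the minute, elapsed time lies between (*n* − 1) days plus 1 minute and *n* days plus 1,439 minutes. The excess therefore lies between 0.0007 and 1.9993 days. For *n* = 1 the condition of more than 24 h keeps the excess below 2 − 1 = 1 day; the wider range applies from *n* = 2.

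**4. The 24-hour condition.** For *n* ≥ 2 the event necessarily exceeds 24 h. For *n* = 1 with a time missing, the condition cannot always be checked, and no rule is given for an untimed next-date event of 24 h or less.

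**The case against.** The duration rules can fairly be defended as a fallback by available precision. Elapsed time cannot be computed without times, the output formats differ visibly, the ongoing-event rule also adds a day, and the duration example is internally correct. That largely stands: 11.4(4) is not contradictory in the way 11.4(5) is. What remains is that an untimed value is a different quantity, shown without a flag, and that its entry condition is sometimes undecidable.

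On onset, the same-date value carries hh:mm when recorded, so a timed same-day event can be recognised. That also stands, and it limits the collision to events without a recorded time. It can also be argued that the example is right and the formula lacks a + 1, since two of the three statements fit an injection day of 1. The text does not settle which was intended, so calling the example simply wrong would go too far. The three statements still cannot all hold.

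A reader might infer that treatment-emergent status or causality is compromised. The documents do not support that. SAP 6.1.2.1 defines treatment emergence by occurrence after injection and within 30 days, not by this derived variable. Relationship is the investigator's assessment and has its own listing column. Nor are the adverse event listings the only safety output: SAP 10.1 also lists laboratory, immunogenicity, pregnancy test, physical examination and vital sign data.

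**Conclusion.** The point holds for delay of onset. SAP 11.4(5) contradicts itself by one day, in two places: the same-date value against the formula, and the partial-date example against the formula. Same-day and next-day onset cannot be told apart when the same-day event has no recorded time, and a partial-date bound can exclude the true delay.

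The duration issue is secondary. It is an unlabelled change of definition worth more than 0 and less than 2 days, with a condition that cannot always be evaluated.

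The consequence is small. The study closed after the first 5 patients, no planned test uses either variable, and only displayed values change. The conclusion assumes that the listings are produced as the shells show, without event dates. If start dates were added, a reader could recover the onset, but the derived column would still be inconsistent. How many events are affected cannot be known from the documents.

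**What to change.** In SAP 11.4(5), apply one convention to the same-date value, the formula and the example, and state that it also covers next-date onset within 24 h. Two choices are coherent:

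- **Injection day = 0:** same day 0, next day 1, example ≥1. This matches Day 0 in SAP 6.1.14 and is the more natural choice.
- **Add 1 throughout:** same day 1, next day 2, example ≥2.

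Under either, show hh:mm where recorded and use the same onset column label in Listings 16.2.7.1 to 16.2.7.4.

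In SAP 11.4(4), flag untimed durations in the listings as inclusive calendar days, and say how an untimed next-date event is handled when the 24-hour condition cannot be checked.

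The cost is a few lines of appendix wording, the matching derivation code, and column headers and footnotes. No new data are needed.
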